5.5.3.1 Drug information

Please refer to [Section 5.5.2](#) for study treatment and the current FDA-approved Investigator's Brochure and the site-specific pharmacy for toxicity information and instructions for drug preparation, handling, and storage.

5.5.4 Obtaining an Investigator's Brochure

Please refer to the current Investigator's Brochure for detailed information regarding olaparib. The olaparib IB can be downloaded from the Members' Area of the NSABP Web site or requested from the CTSU using the CTSU Request for Clinical Brochure Form posted on the CTSU Web site.

5.5.5 Procurement of olaparib (IND #122443, NSC #747856)/placebo

Olaparib (NSC #747856) and matching placebo will be supplied free of charge by AstraZeneca, and will be distributed by the Pharmaceutical Management Branch (PMB), Division of Cancer Therapy Treatment and Diagnosis (DCTD), National Cancer Institute (NCI). PMB policy requires that olaparib/placebo be shipped directly to the institution where the patient is to be treated.

Study supplies are packaged in "kits." Each kit contains 2 bottles of olaparib or matching placebo tablets. The label instructions on each bottle read "Take 1 tablet by mouth twice a day." This consistency of dosing instructions among dose levels is intended to avoid dosing errors for patients receiving 250 mg.

Note: Kits are to be dispensed intact. Do not separate the bottles. Instruct patients to take 1 tablet from each bottle in the kit twice a day.

No blinded starter olaparib/placebo will be available for this study. Blinded, patient-specific olaparib/placebo will be sent to the registering investigator at the time of randomisation and should arrive within approximately 5 business days. Once a patient has been randomised, the NRG Oncology SDMC will electronically transmit a clinical drug request for that patient to the PMB. The request will be processed by the PMB the next business day and shipped the following business day. Shipments will be sent by FedEx Ground (up to 5 business days for delivery but can be expedited by the provision of an express courier account name and number to the NRG Oncology SDMC at the time the patient is randomised. Please note that additional processing time is required for QA/QC checks on patient-specific/blinded orders and next day delivery is not available.

The initial shipment will contain 8 kits (16 bottles) of olaparib or placebo, enough olaparib or placebo to complete 16 weeks of therapy (2 tablets twice a day for 28 days per cycle).

Subsequent orders for blinded, patient-specific supplies must be requested by the Principal Investigator (or his/her authorized designee[s]) for NSABP B-55/BIG 6-13 at each participating institution using the PMB On-line Agent Order Processing (OAOP) program. The assigned patient ID number (e.g., E999999) and the patient initials (e.g., "LFM") should be entered in the "Patient or Special Code" field. A separate order is required for each patient ID number (e.g., E999999) being ordered. All drug orders should be shipped directly to the physician responsible for treating the patient. Requests can be placed **12 weeks after the last shipment is received**. It is recommended that 6 kits (12 bottles) be requested at each order. **The recommended ordering schedule is Weeks 11, 23, and 35.**

Pharmaceutical Management Branch (PMB) policy requires that agent be shipped directly to the institution where the patient is to be treated. PMB does not permit the transfer of agents between institutions (unless prior approval from PMB is obtained). The CTEP-assigned protocol number must be used for ordering all CTEP-supplied investigational agents. The responsible investigator

at each participating institution must be registered with CTEP, DCTD through an annual submission of FDA Form 1572 (Statement of Investigator), Curriculum Vitae, Supplemental Investigator Data Form (IDF), and Financial Disclosure Form (FDF). If there are several participating investigators at one institution, CTEP-supplied investigational agents for the study should be ordered under the name of one lead investigator at that institution.

Active CTEP-registered investigators and investigator-designated shipping designees and ordering designees must submit agent requests through the PMB Online Agent Order Processing (OAOP) application. Access to OAOP requires the establishment of a CTEP Identity and Access Management (IAM) account and the maintenance of an “active” account status and a “current” password. For questions about drug orders, transfers, returns, or accountability, call or email PMB at any time. Refer to the PMB's website for specific policies and guidelines related to agent management.

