5.5.2 Doses and treatment regimens

5.5.2.1 Olaparib and matching placebo (study treatment)

The planned dose of 300 mg b.i.d. (twice daily) will be made up of two (2) x 150 mg tablets b.i.d. (twice daily) with 100 mg tablets used to manage dose reductions as explained in [Table 5](#).

Table 5 Study treatment doses and treatment regimens

Total daily dose	Dose twice daily (b.i.d.)	Morning		Evening	
		Number of tablets	Tablet strength	Number of tablets	Tablet strength
600 mg	300 mg	2 tablets	150 mg	2 tablets	150 mg
Initial dose (300 mg twice daily) can be reduced as follows for AEs (no re-escalation allowed):					
500 mg	250 mg	1 tablet	150 mg	1 tablet	150 mg
		1 tablet	100 mg	1 tablet	100 mg
400 mg	200 mg	2 tablets	100 mg	2 tablets	100 mg
Temporary dose levels due to CYP3A inhibitor exposure (re-escalation allowed):					
300 mg	150 mg	1 tablet	150 mg	1 tablet	150 mg
200 mg	100 mg	1 tablet	100 mg	1 tablet	100 mg

As soon as possible following randomisation, patients will be administered olaparib or matching placebo orally twice daily (b.i.d.) at 300 mg for 52 weeks. Two (2) x 150 mg olaparib or matching placebo tablets should be taken at the same time each morning and evening of each day, approximately 12 hours apart with approximately 240 mL of water. The olaparib/placebo tablets should be swallowed whole and not chewed, crushed, dissolved or divided. Olaparib/placebo tablets can be taken with a light meal/snack (e.g., two pieces of toast or two biscuits).

If vomiting occurs shortly after the study treatment tablets are swallowed, the dose should only be replaced if all of the intact tablets can be seen and counted. Should any patient enrolled on the study miss a scheduled dose for whatever reason (e.g., as a result of forgetting to take the tablets or vomiting), the patient will be allowed to take the scheduled dose up to a maximum of 2 hours after that scheduled dose time. If greater than 2 hours after the scheduled dose time, the missed dose is not to be taken and the patient should take their next allotted dose at the next scheduled time. Patients should not take two doses (4 tablets) at the same time.

Within this study, patients will not be provided olaparib post discontinuation of study treatment. Patients and investigators will not be routinely unblinded to study treatment prior to the final overall survival (OS) analysis.

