5.5.11 Labelling

For **BLINDED (olaparib or placebo) THERAPY**, each bottle will be labeled with:

- the protocol number (i.e., "NSABP-B-55")
- the bottle number (i.e., "Bottle 1 of 2, 2 of 2")
- the number of tablets (i.e., "32 tablets")
- the patient ID number (e.g., "E999999", where "E999999" represents a unique patient identifier assigned by NRG Oncology at registration)
- the patient initials (i.e., last initial, first initial, middle initial [e.g., "L, FM"])
- the agent identification (i.e., "Olaparib 150 mg or Placebo")
- a blank line for the pharmacist to enter the patient's name
- administration instructions (i.e., "Take 1 tablet by mouth twice a day. Discard contents after 90 days")
- storage instructions (i.e., "Store below 30°C (86°F).")
- emergency contact instructions
- a Julian date

The Julian date indicates the day the bottle was labeled and shipped and is composed of the last two digits of the calendar year (e.g., 2013 = 13, 2014 = 14) and a day count (e.g., January 1 = 001, December 31 = 365). For example, a bottle labeled and shipped on January 1, 2013, would have a Julian date of '13001' and a bottle labeled and shipped on December 31, 2014, would have a Julian date of '14365'. The Julian date will be used by PMB for recalls. When a lot expires,

PMB will determine the last date the expired lot was shipped and will recall all bottles (i.e., both Olaparib and Placebo) shipped on or before that date thus eliminating any chance of breaking the blind. The combination Julian Date – Order Number, located in the in the upper right hand corner of the bottle label, should be recorded in the lot number field on the Oral DARF.

Each **BLINDED (olaparib or placebo) KIT BOX** will be labeled with:

- the protocol number (i.e., "NSABP-B-55")
- the patient ID number (e.g., "E999999", where "E999999" represents a unique patient identifier assigned by NRG Oncology at registration)
- the patient initials (i.e., last initial, first initial, middle initial [e.g., "L, FM"])
- the agent identification (i.e., "Olaparib 300 mg or Placebo Kit")
- a blank line for the pharmacist to enter the patient's name
- administration instructions (i.e., "Take 1 tablet from each bottle twice a day.")
- storage instructions (i.e., "Store below 30°C (86°F).")
- emergency contact instructions
- a Julian date

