	Vomiting (despite antiemetics)	2	Maintain dose or ↓ one dose level
		3	↓ one dose level
		4	↓ one dose level or discontinuation
	Infection	3	Hold study therapy: When resolved: Maintain dose or ↓ one dose level Repeat appearance – ↓ one dose level
		4	Hold study therapy: When resolved: ↓ two dose levels or discontinuation
	Dyspnea	1, 2, 3	Hold study therapy; rule out pneumonitis Follow instructions in footnote a
		4	Discontinuation
	Pneumonitis	2	Follow instructions in footnote a
		3, 4	Discontinuation
	Other clinically significant AEs deemed related to study treatment ^{b}	2	Maintain dose or ↓ one dose level
		3	↓ one dose level
		4	↓ two dose levels or discontinuation

^a Hold olaparib/placebo and determine etiology. Unless prohibited based on instructions for other clinical diagnoses (i.e. other AEs), resume olaparib/placebo when grade 0 (if the AE requiring olaparib to be held was dyspnea) or when ≤ grade 1 (if the AE requiring olaparib/placebo to be held was ≥ grade 2).

^b Determination of "clinically significant" AEs is at the investigator's discretion.

Table 8 Dose reduction for study treatment to manage moderate renal impairment

Initial dose	Moderate renal impairment (calculated creatinine clearance by Cockcroft -Gault equation or based on a 24 hour urine test between 31 and 50 ml/min): Dose reduction
300 mg twice daily	200 mg twice daily

Table 9 Dose reduction for study treatment with concurrent use of a strong or moderate CYP3A inhibitor

Initial dose	Strong CYP3A inhibitor	Moderate CYP3A inhibitor
300 mg twice daily	100 mg twice daily	150 mg twice daily

For guidance on dose reductions for management of renal impairment refer to [Section 5.5.12.3](#),

For guidance on dose reductions when concomitant strong or moderate CYP3A inhibitors cannot be avoided see [section 5.6.2](#).

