5.6.2 Restricted concomitant medications

The use of any natural/herbal products or other traditional remedies should be discouraged but use of these products, as well as any medication or vaccine including over-the-counter or prescription medicines, vitamins, and/or herbal supplements that the patient is receiving at the time of enrolment or receives during the study must be recorded along with:

- Reason for use
- Dates of administration including start and end dates
- Dosage information including dose and frequency

Table 10 Restricted concomitant medications

Medication/class of drug:	Usage (including limits for duration permitted and special situations in which it's allowed):

Strong CYP3A inhibitors: itraconazole, telithromycin, clarithromycin, boosted protease inhibitors, indinavir, saquinavir, nelfinavir, boceprevir, telaprevir
	
Strong or moderate CYP3A inhibitors should not be taken with study treatment. If there is no suitable alternative concomitant medication then the dose of study treatment should be reduced for the period of concomitant administration. The dose reduction of study treatment should be recorded in the CRF with the reason documented as concomitant CYP3A inhibitor use.

Moderate CYP3A inhibitors: ciprofloxacin, erythromycin, diltiazem, fluconazole, verapamil
	
 • Strong CYP3A inhibitors — reduce the dose of study treatment to 100 mg b.i.d for the duration of concomitant therapy with the strong inhibitor and for 5 half-lives afterwards. • Moderate CYP3A inhibitors - reduce the dose of study treatment to 150 mg b.i.d for the duration of concomitant therapy with the moderate inhibitor and for 3 half-lives afterwards. • After the washout of the inhibitor is complete, the study treatment dose can be re-escalated.

Strong CYP3A inducers: phenobarbital, phenytoin, rifampicin, rifabutin, rifapentine, carbamazepine, nevirapine, enzalutamide and St John's Wort
	
Strong or moderate CYP3A inducers should not be taken with study treatment.
 
If the use of any strong or moderate CYP3A inducers are considered necessary for the patient's safety and welfare this could diminish the clinical efficacy of olaparib.

Moderate CYP3A inducers: bosentan, efavirenz and modafinil
	
If a patient requires use of a strong or moderate CYP3A inducer then they must be monitored carefully for any change in efficacy of study treatment.

Table 10 Restricted concomitant medications

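### The US kit instructions (intact kits, one tablet from each of two bottles) cannot deliver the 150 and 100 mg b.i.d. doses required with a CYP3A inhibitor, and no exception is written

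*Protocol*

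**What the plan says.** **The dose.** Section 5.6.2, Table 10, discourages strong and moderate CYP3A inhibitors but provides for unavoidable use: "If there is no suitable alternative concomitant medication then the dose of study treatment should be reduced for the period of concomitant administration". For strong inhibitors the site must "reduce the dose of study treatment to 100 mg b.i.d for the duration of concomitant therapy with the strong inhibitor"; for moderate ones, "reduce the dose of study treatment to 150 mg b.i.d for the duration of concomitant therapy with the moderate inhibitor". Table 9 in Section 5.5.12.2 ("Dose reduction for study treatment with concurrent use of a strong or moderate CYP3A inhibitor") gives the same two doses from a 300 mg starting dose, and Table 6 lists them as dose levels. Table 5 in Section 5.5.2.1 spells out the tablets under "Temporary dose levels due to CYP3A inhibitor exposure (re-escalation allowed"): one 150 mg tablet or one 100 mg tablet, morning and evening.

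**The supply.** Section 5.5.3 defines three kits, each of two 32-tablet bottles: 300 mg (150 + 150), 250 mg (100 + 150) and 200 mg (100 + 100). Section 5.5.5 requires kits to be dispensed intact and adds "Do not separate the bottles. Instruct patients to take 1 tablet from each bottle in the kit twice a day". Under Section 5.5.11 the kit box carries "Take 1 tablet from each bottle twice a day" and the bottles are numbered "Bottle 1 of 2, 2 of 2". Section 5.5.6, on ordering after a dose reduction, names orders for the 250 and 200 mg kits only.

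In the other direction, the label on each single bottle tells the patient to take one tablet twice a day.

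**The concern.** Two written rules meet at the same patient and cannot both be obeyed. The dosing tables require one tablet per intake; the dispensing rule and the box require two. Section 5.6.2, to which the reader is sent for CYP3A reductions, is silent on kits, bottles and ordering.

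The bottle label does not settle the matter. A patient with two bottles, each saying one tablet, in a box saying one from each, is being told to take two. The label gives the right dose only if one bottle is withheld, and Section 5.5.5 forbids that.

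The temporary levels exist to prevent over-exposure while an interacting drug is taken, so an instruction that leads to the higher dose defeats the safeguard. Section 13.2 gives the tablet MTD as 300 mg b.i.d. and treats any dose above the protocol regimen as a reportable overdose. A patient who obeyed the box during inhibitor use would therefore generate one.

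**Working it through.** **Inputs**
- Kits, 32 tablets per bottle and a 16-day supply per kit: Section 5.5.3.
- One tablet from each of two bottles, twice a day: Sections 5.5.5 and 5.5.11.
- Required doses of 150 mg (moderate) and 100 mg (strong) b.i.d.: Tables 5, 6, 9 and 10.
- First-shipment timing: Section 5.5.5. Four-week limit on holding drug: Section 5.5.12.
- About 230 US patients, randomised 1:1: Synopsis.

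**The plan's own figure.** 2 bottles × 32 tablets = 64 tablets; 4 tablets a day; 64 / 4 = 16 days. This reproduces the stated kit supply and confirms that the kit is built for two tablets per intake.

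**Doses reachable under the kit rule**, compared with the dose required:

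| Kit | Dose b.i.d. | Ratio to 150 mg (moderate) | Ratio to 100 mg (strong) |
|---|---|---|---|
| 300 mg | 150 + 150 = 300 | 2.00 | 3.00 |
| 250 mg | 100 + 150 = 250 | 1.67 | 2.50 |
| 200 mg | 100 + 100 = 200 | 1.33 | 2.00 |

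The minimum is 200 mg b.i.d., so neither required dose can be reached. For the 300 mg starting dose listed in Table 9 the worst case is 2.0 or 3.0 times the required tablet dose.

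**If a single bottle were allowed.** One bottle at 1 tablet b.i.d. lasts 32 / 2 = 16 days. The 300 mg kit already holds 150 mg tablets, so a moderate inhibitor needs no new order while one such bottle lasts, and longer if further kits from the 8-kit first shipment are on hand. The kit holds no 100 mg tablets, so a strong inhibitor needs an order.

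**Waiting time for that order.** Assumption: it takes as long as the first shipment. About 5 business days is 7 calendar days. The maximum is 1 (processing) + 1 (shipping) + 5 (delivery) = 7 business days, or 9-11 calendar days. Against the 28-day limit the margin is 28 − 11 = 17 to 28 − 7 = 21 days, so a hold is feasible.

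**Leftover kit.** After 7 days on one bottle, 32 − 14 = 18 tablets remain in it against 32 in the other, so the pair no longer matches on re-escalation.

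**Number of patients.** 230 / 2 = 115 on olaparib. Assumption, since the protocol gives no rate: if 2-10% need such an inhibitor, 115 × 0.02 = 2.3 to 115 × 0.10 = 11.5, or about 2-12 patients.

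**The case against.** The best defence is that the dose itself is clear. Table 5 states tablet number and strength for both levels, and a specific dosing table would normally be read as overriding a general packaging note. Over-dosing would need several safeguards to fail at once: the reduction and its reason go in the CRF, patients must receive clear instructions, and tablets are counted. These inhibitors are excluded at entry and allowed later only without a suitable alternative, and a site without the right bottle can hold drug.

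Section 5.5.6 is also plainly not exhaustive. It omits the direct step from 300 to 200 mg that Tables 7 and 8 call for, and it expresses orders as bottles by strength, so a single-bottle request is not prohibited. Accountability is partly covered already, since records are kept by patient and tablet strength.

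Most of this stands, and it limits the likely harm. The ratios are of tablet dose, not exposure, and describe a worst case. But none of it supplies the missing exception. A site that follows Table 5 must break an explicit instruction not to separate the bottles, and must improvise the order, the label and the patient instruction in a blinded trial.

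**Conclusion.** The concern holds. Within the US protocol the intact-kit rule and the temporary CYP3A-inhibitor doses are incompatible, and the text contains no exception. The lowest dose under the kit rule is 200 mg b.i.d. against a required 150 or 100 mg b.i.d.; from the starting kit the worst-case excess is 2.0-fold or 3.0-fold.

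The practical reach is small. The range of about 2-12 olaparib patients facing conflicting instructions rests wholly on the assumed 2-10% rate, and the number over-dosed would be lower. This is a matter of dosing safety and supply, and has no bearing on the efficacy endpoints, power or type I error. It should be corrected because a dosing safeguard is contradicted outright and the correction is cheap.

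**What to change.** - **Sections 5.5.5 and 5.5.11:** limit the intact-kit, one-from-each-bottle rule to the 300, 250 and 200 mg levels.
- **Section 5.5.6:** for 150 or 100 mg b.i.d., have the site dispense one bottle of that strength without the kit box. If that strength is not in hand, the site requests it through OAOP under the same special procedure and holds study drug, within the 4-week limit, until it arrives.
- **Label:** mark that bottle as a single bottle, or give the patient a written instruction that replaces the box text.
- **Re-escalation:** dispense a new intact kit, and say how the unused bottle is stored and counted, with reference to the existing accountability records.

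The blind is preserved because Table 4 provides matching placebo in both strengths. The cost is a few sentences and a label or short patient instruction; the tablets and bottles already exist. The downsides are an occasional part-used kit, a separate count instruction and, for a few patients, about 7-11 days of missed doses if a bottle must be ordered.

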5.5.6 Special ordering procedures for patients requiring a dose reduction

If the patient is **dose reduced** from 300 mg b.i.d. to 250 mg b.i.d. (or 250 mg b.i.d. to 200 mg b.i.d.), an agent request must be submitted by the site through the OAOP application.

- For each 250 mg kit, request 1 bottle of 100 mg tablets and 1 bottle of 150 mg tablets.
- For each 200 mg kit, request 2 bottles of 100 mg tablets.

The number of kits included in the initial shipment will depend on the patient's place on the treatment calendar.

5.5.7 Agent inventory records

The investigator, or a responsible party designated by the investigator, must maintain a careful record of the receipt, dispensing and final disposition of all agents received from the PMB using the appropriate NCI Investigational Agent (Drug) Accountability Record (DARF) available on the CTEP forms page. Store and maintain separate NCI Investigational Agent Accountability Records for each agent, strength, formulation and ordering investigator on this protocol.

5.5.9 Transfer of olaparib/placebo

Kits/bottles may **not** be transferred from one patient to another patient or from one protocol to another protocol. PMB does not permit the transfer of agents between institutions (unless prior

approval from PMB is obtained). Olaparib/placebo may not be used outside the scope of this protocol, nor can olaparib/placebo be transferred or licensed to any party not participating in this clinical study. To obtain an approval for transfer, investigators should complete and submit to the PMB ([contact]) a Transfer Investigational Agent Form available on the NCI home page (<http://ctep.cancer.gov>) or call the PMB at [contact]. The participating institution should also inform the NRG Oncology SDMC of the transfer.

5.5.10 Return of olaparib/placebo

At the completion of accrual and treatment, all unused (unopened) bottles of olaparib/placebo must be returned to the PMB. When it is necessary to return study drug (e.g., unused bottles remaining when the protocol is closed to accrual and treatment at a participating clinical site or unopened expired bottles), investigators should return the olaparib/placebo to the PMB using the NCI Return Agent Form available on the NCI home page (<http://ctep.cancer.gov>) or call the PMB at [contact].

Tablets remaining from dispensed bottles should be documented on the patient-specific NCI Investigational Agent Accountability Record Form for Oral Agents. On the correct dispensing row, document the date returned and the quantity, then destroy on site in accordance with institutional policy.

